1.0 Objectives

1.1 Study Objectives

The specific aims of the current study are to:

1) Examine the longitudinal effect of very low nicotine content (VLNC) cigarettes on changes in task-related functional neural activation within brain circuitry associated with incentive salience valuation and executive function. We hypothesize that, for the VLNC group compared to the normal nicotine content (NNC) group:

- a. Reactivity to smoking vs. pleasant odors within incentive salience circuitry will decrease.
- b. Reactivity to monetary rewards within incentive salience circuitry will increase.
- c. Activity during decision-making and inhibitory control within executive control circuitry will increase.

2) Assess the longitudinal effect of VLNC cigarettes on changes in effective (directional) connectivity between incentive salience and executive control brain circuitry. We hypothesize that, for the VLNC group compared to the NNC group:

- a. The influence of executive control over incentive salience circuitry, measured during task demands that simultaneously engage both processes, will increase.
- b. The influence of non-smoking reward salience circuitry over smoking salience circuitry during the odor cue reactivity task will increase.

3) Establish measurable and objective neural outcomes of successful reductions in smoking dependence.

1. We hypothesize that changes in functional activation and effective connectivity over the course of the VLNC intervention will be correlated with reductions in subjective and behavioral assessments of smoking dependence, including the number of cigarettes smoked per day, subjective reports of dependence, craving, and withdrawal.

4) Assess the effect of VLN Cigarettes vs NNC cigarettes on the levels of salivary miRNAs targeting dopamine, glutamate, acetylcholine and GABA-related transcripts over 6-weeks.

1. We hypothesize that the VLNC group will have significantly more changes in miRNA expression than the NNC group. A two-way repeated measures ANOVA will be conducted to compare changes in miRNA expression over three time points for the VLNC and NNC groups.

5) Determine if within-subject changes in miRNA expression are associated with changes in fMRI BOLD signal during smoking cue-reactivity and inhibitory control tasks for the VLNC group over 6-weeks.

1. We hypothesize that salivary levels of miRNAs with putative targets in the nicotine addiction pathway will be associated with decreased corticostriatal cue-reactivity and increased ventromedial and dorsolateral prefrontal cortex engagement during inhibitory control in the VLNC group compared to the NNC group.

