We currently know little about how neural activity and connectivity of the incentive salience and executive control circuitry change during cessation treatment. Given the advancements in pharmacotherapy and non-invasive brain stimulation techniques,^{30,31} gaining a nuanced understanding of how brain circuitry adapts during rehabilitation could identify neural targets for treatment. Verenicline and bupropion treatment are associated with reductions in neural activity throughout prefrontal brain circuitry during executive control and cue-reactivity tasks, respectively.^{32,33} However, given the reductions in dependence for the control groups, these neural changes were likely due to the effects of the medication, not changes in dependence.^{32,33} Very low nicotine content (VLNC) cigarettes have been used as an extinction-based cessation treatment to reduce the rewarding effects of cigarettes by significantly reducing nicotine delivery during smoking.^{6,34} Smokers rate de-nicotinized cigarettes as satisfying and trials of VLNC cigarettes result in decreases in the number of cigarettes smoked per day and self-reported dependence.³⁵ VLNC cigarettes provide a unique opportunity to assess changes in neural circuitry while smokers extinguish the association between nicotine and smoking stimuli and become less dependent on smoking without the confounding effects of nicotine replacement therapy or pharmacotherapy.

The current study will examine functional neuroadaptations in incentive salience and executive control circuitry while smokers switch to VLNC cigarettes over 6-weeks. Identifying brain circuitry that is

modified at various stages of recovery can lead to the development of targeted neuropharmacological cessation aids and brain stimulation techniques. The findings of the proposed study will characterize changes associated with the extinction of conditioned cues and reductions in dependence without the confounding effects of pharmacological aids. By measuring neural processes and connectivity among circuitry mid-intervention, the results of the proposed study will pinpoint aspects of neural circuitry that are sensitive to (or reflective of) early intervention effects.

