5. At the end of the visit, participants will be asked to keep a log of the cigarettes they smoke each day until their next visit. Participants will receive a daily REDCap survey link via text message using the Twilio service. The survey will ask participants to record the frequency and type of tobacco and alcohol used that day. Participants will be instructed on how to complete the survey and will be provided with a paper log to tally their cigarette use throughout the day. Participants who are unable or unwilling to receive study text messages will track their cigarette use on the paper log only. The REDCap or paper daily cigarette log surveys are not mandatory for participation.

Time commitment: 1.5 hour

Participants will be asked to refrain from smoking for 14 hours prior to MRI Visit 1. A Zoom call (**Remote Visit 1**) and In-person visit (**MRI Visit 1**) will be scheduled.

7.2.2 MRI visit 1

Participants will complete the following procedures in person after refraining from smoking for 14 hours prior to the visit.

Participants will sign their long form written consent at this visit prior to any further study procedures.

1. REDCap Survey Questionnaire
 - a. Nicotine Withdrawal (MNWS)
 - b. Smoking Urges (QSU)
 - c. Craving questionnaire
2. Interview
 - a. Penn State CNMRR MRI Safety
 - b. Scent Ratings post MRI Scan
3. Biomarkers
 - a. Urine collection for cotinine analysis and pregnancy determination: Obtain urine and process pregnancy test for women of child bearing age (have had a period in the past 12 months) who have not had a hysterectomy.
 - b. Saliva collection for potential cotinine analysis, micro RNA (miRNA) biomarker analysis and use in future research.
 - c. Exhaled carbon monoxide will be measured using a hand-held monitor.

4. A member of the study team will first review the MRI safety sheet and determine that it is safe for the participant to be scanned. If safe, participants will complete a one-hour MRI scan that will include the following tasks.

The risks and discomforts associated with this project are the same as that associated with standard clinical MRI and EEG studies, which are minimal. Risk exists from radio frequency heating of the head, but is safe at the specific absorption rate (SAR) limits prescribed by the FDA. The SAR of radiofrequency field exposure is monitored throughout the study and maintained below the limits established by the FDA.

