7.2.5 Remote visit 2 (Week 3 ± 5 days)

Participants will complete a Zoom call three weeks into the randomization phase. During this visit participants will complete the following activities:

1. Review cigarette tracking logs with study staff.
2. Concomitant medication
3. Adverse event trigger questions
4. Discuss and problem-solve barriers to adherence
5. Computerized REDCap Survey Questionnaires (see Remote Visit 1 and MRI Visit 1)
6. Complete computerized out-of-scanner tasks.

Time commitment: 1 hours

Participants will be asked to refrain from smoking for 14 hours prior to MRI visit 2. The MRI visit 2 and Remote visit 3 will be scheduled.

7.2.6 Phone call 2

Participants will be contacted in the 4th week of the randomization phase to check-in regarding their next scheduled appointment and their success with cigarette tracking and study cigarette compliance.

Time commitment: 15 minutes

7.2.7 Remote visit 3 (scheduled for -1 to +1 day of in person MRI visit)

Participants will complete the following procedures over a Zoom call

1. Concomitant medications
2. Adverse event trigger questions
3. Perceived health risk rating
4. Computerized REDCap Survey Questionnaires (see Remote Visit 1)
5. Review cigarette tracking logs.
6. Complete computerized out-of-scanner tasks
7. Complete quit choice survey and counseling. Participants will be reminded that they will receive a text message survey in 12 weeks asking for information on quit attempts.

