7.2.8 MRI visit 2 (Week 6 ± 5 days)

Participants will return to the CNMRR Center for their final MRI scan after refraining from smoking for 14 hours prior to the visit.

For the final study visit, participants will complete the following activities:

1. Return all (empty and full) cigarettes packs
2. Penn State CNMRR MRI safety and Scent Ratings (post MRI)
3. Urine collection for cotinine analysis and pregnancy determination: Obtain urine and process pregnancy test for women of child bearing age (have had a period in the past 12 months) who have not had a hysterectomy
4. Saliva collection for potential cotinine analysis, micro RNA (miRNA) biomarker analysis, and use in future research.
5. Exhaled carbon monoxide will be measured using a hand-held monitor.
6. Computerized REDCap Survey Questionnaires (nicotine withdrawal, smoking urges, craving)
7. The MRI technologist will first review the MRI safety sheet and determine that it is safe for the participant to be scanned. If safe, participants will complete a one-hour MRI scan.

Time commitment: 2 hours

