7.4.4 Subject Compliance Monitoring

Participants will track the number of cigarettes they smoke each day in the REDCap surveys sent to them via text message and using a paper tally tracking log. Participants will be given detailed instructions on how to complete the logs and they will be reminded at each study contact to only use the research cigarettes they have been given. Questions will be asked at each contact to review their log and verify how many cigarettes they are smoking each day. Participants will also be asked to self-report their other tobacco use including products such as cigars, pipes, chew, snus, dip, hookah, electronic cigarettes and dissolvable tobacco. Exhaled carbon monoxide measurements, urine, and saliva will be taken at each contact to verify smoking intensity and cotinine levels.

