Aim 3: Establish measurable and objective neural outcomes of successful reductions in smoking dependence. FSL's Randomise one-sample t-test will be conducted on change scores to determine if changes in BOLD activity are associated with reductions in subjective markers of dependence (FTND, HONC, MNWS, QSU), cigarettes smoked per day, and quit intention and success. Changes in connectivity estimates will be correlated with changes in subjective and behavioral outcomes.

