16.0 Resources Available

16.1 Facilities and locations

All in-person participant visits will take place in the Center for NMR Research. Urine and saliva specimens will be stored, processed and analyzed in the Biomarkers and Analytical Chemistry Core (BACC) laboratory on the 3rd floor of the Cancer Institute or sent to another Biosafety approved HMC laboratory if the BACC does not have capacity. These laboratories will not charge participants or insurance organizations for analysis procedures.

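### Aim 4 plans its salivary miRNA ANOVA over three time points, but the visit procedures list miRNA saliva at only two visits and no other text establishes a third

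*Combined protocol and SAP*

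**What the plan says.** Section 1.1 gives the only analysis stated for Aim 4: "A two-way repeated measures ANOVA will be conducted to compare changes in miRNA expression over three time points for the VLNC and NNC groups".

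The visit procedures name miRNA saliva in two places:

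- MRI visit 1 (7.2.2): "Saliva collection for potential cotinine analysis, micro RNA (miRNA) biomarker analysis and use in future research".
- MRI visit 2, week 6 (7.2.8): "Saliva collection for potential cotinine analysis, micro RNA (miRNA) biomarker analysis, and use in future research".

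For the week-3 visit (7.2.5), "Participants will complete a Zoom call three weeks into the randomization phase". Its activity list covers logs, medication, adverse events, adherence, questionnaires and computer tasks, with no specimen.

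Section 7.4.4, on compliance, reads differently: "Exhaled carbon monoxide measurements, urine, and saliva will be taken at each contact to verify smoking intensity and cotinine levels".

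Section 8.3 sets out methods aim by aim, and the last one is "Aim 3: Establish measurable and objective neural outcomes of successful reductions in smoking dependence". Aims 4 and 5 do not appear there.

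**The concern.** A planned analysis and its data schedule should have the same number of occasions. Here the analysis has three and the visit lists have two, and the statistical section that should settle the count is silent on Aim 4.

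Two explanations are open. Either the word three does not belong in Aim 4, or a week-3 saliva collection was meant and left out of 7.2.5. The consequences differ. The first is a wording error. In the second, the sample cannot be recovered from any participant who has already passed week 3. The documents do not say which applies.

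**Working it through.** **Step 1: count the scheduled miRNA specimens (sections 7.2.1 to 7.2.8 and the week-18 survey).**

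| Contact | Mode | miRNA saliva listed |
|---|---|---|
| Final screen | Zoom | No (biomarker item is the smell test only) |
| MRI visit 1 | In person | Yes |
| Remote visit 1 | Zoom | No |
| Phone call 1 | Phone | No |
| Remote visit 2 (week 3) | Zoom | No |
| Phone call 2 | Phone | No |
| Remote visit 3 | Zoom | No |
| MRI visit 2 (week 6) | In person | Yes |
| Week-18 survey | Text message | No |

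The total is 2, against 3 in Aim 4.

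**Step 2: see whether 7.4.4 supplies the third.** The result depends on what counts as a contact.

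- *In-person contacts, with screening remote as in 4.4, 5.2.2 and 7.2.1.* There are two, both at the imaging centre, in line with section 16.1: "All in-person participant visits will take place in the Center for NMR Research".
- *In-person contacts, with screening in person.* Section 4.2 describes the screening visit as in person, and section 11.0 places a urine pregnancy test at screening. That would make three in-person contacts. The screening sample would precede treatment, however, and 7.2.1 lists no saliva.
- *All contacts.* This would include week 3. Remote visit 1 falls 1 to 3 days after MRI visit 1, and Remote visit 3 falls within a day of MRI visit 2. Leaving aside screening, the phone calls and the text survey, contacts then cluster at baseline, week 3 and week 6. No section says how saliva, urine or exhaled CO would be taken over Zoom or by phone.

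So 7.4.4 conflicts with the visit lists and can be read in more than one way. No reading is backed by a listed third miRNA collection.

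**Step 3: size of the mismatch if the visit lists govern.**

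- Specimens at 75 completers (8.1): 75 × 3 = 225 planned, 75 × 2 = 150 scheduled.
- Specimens at the 60 in the 80% retention scenario of 8.2: 60 × 3 = 180 against 60 × 2 = 120.
- Arm-by-time numerator degrees of freedom, (groups − 1)(occasions − 1): (2 − 1)(3 − 1) = 2 planned, (2 − 1)(2 − 1) = 1 available.

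With two occasions, the arm-by-time test is the two-group comparison of change scores. It is valid, but it carries no information about the course between baseline and week 6.

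**Step 4: precision of a baseline-adjusted analysis on the two scheduled samples.** Let ρ be the correlation between baseline and week-6 levels, with equal variance σ² at both visits (both are assumptions; the documents give neither).

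- Change-score variance per participant: 2σ²(1 − ρ).
- ANCOVA residual variance per participant: σ²(1 − ρ²).
- Ratio: (1 − ρ²) / [2(1 − ρ)] = (1 + ρ)/2.
- At ρ = 0.3, 0.5 and 0.7 the ratio is 0.65, 0.75 and 0.85.

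The ratio does not exceed 1 for any ρ, ignoring the few degrees of freedom spent on covariates.

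**The case against.** The strongest reply rests on 7.4.4. Taken literally, saliva is collected at week 3 too. Its stated purpose of checking cotinine does not rule out miRNA, because in 7.2.2 and 7.2.8 the same saliva serves both. This part stands: 7.4.4 cannot be dismissed as irrelevant, and the statement that a three-level factor cannot be fitted holds only if the visit lists prevail. But a general compliance sentence with no remote collection method does not establish a week-3 miRNA specimen.

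A reader might go further and infer that a week-3 collection was certainly planned and then dropped. Three pieces of text invite this, and none supports it:

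- The sample sizes in 8.2 (28, 86 and 28) are reproduced by a standard repeated measures calculation with three measurements, if one assumes two equal groups and a correlation of 0.5. Section 8.2 ties those figures to behavioural data, however. Questionnaires and out-of-scanner tasks are scheduled at three waves (Remote visits 1, 2 and 3), so the match says nothing about saliva.
- Section 2.1 has the wording "By measuring neural processes and connectivity among circuitry mid-intervention". This concerns neural measures.
- The 3-week visit mentioned in 8.2 is Remote visit 2, which exists and lists no specimen.

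It can also be said that miRNA is neither a primary endpoint (1.2) nor a secondary one (1.3 lists none), and that if two visits are intended the repair is close to changing one word. That is fair, and it sets the rating.

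**Conclusion.** The mismatch is real. Aim 4's only stated analysis uses three miRNA time points, the visit procedures schedule two, and nothing else in the protocol establishes a third. If the visit lists govern, the analysis cannot be run as written: one of three occasions is missing, and the arm-by-time test has 1 degree of freedom instead of 2.

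The point is minor. It reaches Aim 4 and the miRNA data that Aim 5 draws on, and it leaves the primary endpoints alone. The type of test is not at fault, since repeated measures ANOVA works with two levels. A reader might infer that Aim 4 is underpowered as a result. The documents give no miRNA effect size, so no statement about its power can be made either way. The irrecoverable loss of samples is conditional on a week-3 collection having been intended, which is not shown.

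**What to change.** Reconcile Aim 4 in 1.1 with 7.2.2, 7.2.5, 7.2.8 and 7.4.4. In 7.4.4, say which contacts are meant for CO, urine and saliva. Reconcile 4.2 and 11.0 with 4.4, 5.2.2 and 7.2.1 on whether screening is in person or remote. State the Aim 4 analysis in 8.3. The rest depends on intent.

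- **If two visits are intended.** Restate Aim 4 for baseline and week 6. Either keep the named ANOVA and test arm by time, or use ANCOVA of the week-6 level on arm, baseline level and gender (the stratification factor in 7.4.3). ANCOVA uses only data already scheduled. Under the assumptions in the working, its variance is 0.65 to 0.85 of that of the change-score test. The cost is a text amendment, with no new visits or samples. The plan gives up a mid-point that the visit lists do not collect.
- **If a week-3 sample is intended.** List it in 7.2.5 together with the way it is collected at a Zoom visit, and keep three time points. Applied to the whole trial, this adds at least 75 specimens (one per completer) and up to about 90 (the expected enrolment in 8.1, since some who give a week-3 sample may later drop out), plus collection and assay costs. Participants already past week 3 would lack that point, and the analysis would have to allow for it.

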1.2 Primary Study Endpoints

Changes in neural reactivity to tobacco odor and changes in smoking dependence.

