- Prior to the visit, an unblinded member of the study team will randomize the participant to either the VLNC or NNC cigarette group based on a pre-determined block randomization list. The unblinded study member will identify the cigarette packs with the assigned nicotine content by NRC code and prepare them for redistribution by re-labeling each pack with the participant ID number and a label indicating these are research cigarettes. The unblinded study member will keep records of the RTI log numbers of the packs dispensed to each participant at each visit. At the end of MRI Visit 1 participants will be given an ample 6-week supply of their assigned cigarette (125% of baseline cigarettes per day) and instructed to only smoke study cigarettes until their next scheduled appointment. Participants may contact the study team to receive more study cigarettes if they run out prior to their next visit unless this is more than a 100% increase from their baseline CPD. Participants will be instructed to continue completing the daily REDCap cigarette log surveys that they receive via text message and will also be given paper cigarette logs to track use throughout the day.

Time commitment: 2 hours

7.2.3 Remote visit 1 (scheduled for +1 to +3 day(s) of in person MRI visit)

Participants will complete the following procedures over Zoom

1. REDCap Survey Questionnaire

- a. Depression (CESD)
- b. COPD (CCQ)
- c. Psychological Distress (Kessler K6)
- d. Nicotine Dependence
- e. Anxiety (ASQ)
- f. Sleep Disturbance
- g. Cigarette Liking
- h. Stages of Change
- i. Perceived Stress

2. Interview

- a. Concomitant medications
- b. Adverse event trigger questions

3. Out of scanner tasks

- a. Participants will complete a monetary temporal discounting task. During this computerized task, participants will choose between two options with specified dollar amounts and time delays to receipt of money (see MRI task image below).
- b. Participants will complete a computerized stroop interference task where they will view color words printed in the same color (i.e., blue, red, yellow, green), color words printed in an incongruent color (e.g., “blue” printed in red), and color neutral words printed in color (e.g., “hat” printed in red). Participants will be asked choose what color each word is printed in by pressing a button labeled to indicate each color.

7.2.4 Phone call 1

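### Change in smoking dependence is a primary endpoint, but no listed analysis compares it between arms, and the Nicotine Dependence questionnaire is first listed after cigarettes are dispensed

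*Combined protocol and SAP*

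**What the plan says.** Section 1.2 names two primary endpoints: "Changes in neural reactivity to tobacco odor and changes in smoking dependence". It gives no dependence instrument, time point or order of testing. Section 1.3 lists no secondary endpoints.

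In 8.3, dependence appears only under Aim 3. A one-sample test on change scores is run "to determine if changes in BOLD activity are associated with reductions in subjective markers of dependence", with FTND, HONC, MNWS and QSU listed, together with cigarettes per day and quit intention and success. Then: "Changes in connectivity estimates will be correlated with changes in subjective and behavioral outcomes". The matching hypothesis in 1.1 also predicts correlation only.

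On timing, 7.2.2 states: "At the end of MRI Visit 1 participants will be given an ample 6-week supply of their assigned cigarette". The item called Nicotine Dependence is first listed at Remote visit 1 (7.2.3), which is "scheduled for +1 to +3 day(s) of in person MRI visit".

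**The concern.** A randomised trial supports a causal statement about an endpoint through the comparison of its arms. For dependence, none is listed. Change from baseline cannot stand in for it: section 2.1, on earlier medication studies, discounts a dependence explanation of the neural changes "given the reductions in dependence for the control groups". Nor can a correlation between BOLD change and dependence change show that VLNC cigarettes reduced dependence, because it contains no arm contrast.

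The choice of score is also open. With at least five candidate measures in 8.3 and none named in 1.2, the one reported as primary could be picked after the data are seen.

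The baseline matters because a score taken after participants have received their assigned cigarettes is no longer a pure covariate. Part of any early treatment effect may sit in it, and would then be subtracted or adjusted away, or added.

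**Working it through.** **Which outcomes have an arm-level analysis?**

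- BOLD activation: yes. 8.3 Aim 1 has mixed models covering within- and between-subject treatment-related change.
- Connectivity: yes. 8.3 Aim 2 has a mixed-effects ANOVA with between-subjects effects.
- miRNA: yes. 1.1 Aim 4 has a two-way repeated measures ANOVA by group.
- Dependence: no. 8.3 Aim 3 is association only. The consumption test in 10.7 is a paired pre/post test, and its data are not reviewed across arms unless the principal investigator asks for an unblinded safety analysis.

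**Which dependence measures have a value before dispensing?**

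- Nicotine Dependence questionnaire: first listed at Remote visit 1, after dispensing; repeated at Remote visits 2 and 3.
- MNWS and QSU: listed at MRI visit 1 (cigarettes are handed out at its end) and at MRI visit 2, both after 14 hours without smoking.
- Cigarettes per day: the log starts at the remote screen, but is not mandatory (7.2.1).
- WISDM-Brief: at the remote screen, with no later repeat listed and not among the 8.3 measures.
- Tobacco use history: at the remote screen; whether it holds dependence items is not stated.
- FTND and HONC: named in 8.3 but in no visit list, so whether either is the Nicotine Dependence item is not stated.

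**The plan's own figures (8.2).** For f = 0.25, 80% power and alpha 0.05 it gives 28 (within), 86 (between) and 28 (interaction). These reproduce if one assumes two equal groups, m = 3 measurements and correlation 0.5:

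- Between: noncentrality N·f²·m/(1+(m−1)ρ) = 86 × 0.0625 × 3/2 = 8.06, power 0.801.
- Within and interaction: N·f²·m/(1−ρ) = 28 × 0.0625 × 3/0.5 = 10.5, power 0.812.

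The figures are for behavioural data generally; 8.2 does not tie them to dependence.

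**Power of the missing comparison.** The documents give no expected arm difference in dependence or baseline correlation, so both are assumed. Noncentral t, two-sided; noncentrality = d/√(1/n₁+1/n₂); ANCOVA replaces d by d/√(1−ρ²) and loses two degrees of freedom for baseline and gender. Sizes are 50/25, and 40/20 for the n = 60 case in 8.2, with losses assumed equal across arms.

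- Scale factor √(1/n₁+1/n₂): 0.245 at 50/25, 0.274 at 40/20.
- Unadjusted, d = 0.5: 0.5/0.245 = 2.04, power 0.522; at 40/20, 0.5/0.274 = 1.83, power 0.435.
- Unadjusted, d = 0.3 and 0.8: 0.227 and 0.897 at 50/25; 0.190 and 0.819 at 40/20.
- ANCOVA, d = 0.5, ρ = 0.3/0.5/0.7: noncentrality 2.14/2.36/2.86, power 0.560/0.642/0.805 at 50/25; 0.469/0.545/0.710 at 40/20.
- ANCOVA, d = 0.5, ρ = 0.5, alpha 0.025 (if alpha were split between two primary endpoints): 0.529 and 0.428.
- Difference detectable with 80% power at alpha 0.05: 0.70 SD unadjusted and 0.60 SD with ANCOVA at ρ = 0.5 (50/25); 0.78 and 0.68 SD (40/20).

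**Effect of a post-dispensing baseline.** If it already holds a fraction f of the week-6 effect, a change score estimates (1−f) of that effect and ANCOVA estimates (1−ρf). At ρ = 0.5:

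- f = +0.25: 75% (change score) and 87.5% (ANCOVA).
- f = −0.25, an early shift the other way: 125% and 112.5%.

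Both the size and the sign of f are assumptions.

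**The case against.** The strongest reply is that no aim sets out to show that VLNC cigarettes reduce dependence. Section 2.3 treats dependence as something neural markers should track, 2.2 cites a large earlier trial for the reduction itself, and 8.2 describes the design as pilot data. On that view the defect is a mismatch between 1.2 and the aims, and one corrected sentence cures it. This stands as an alternative remedy. It does not excuse leaving 1.2 as it is, and future sizing from pilot data would itself need a between-arm estimate.

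Four stronger readings are tempting, and the documents do not support them.

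- *That Aim 1 has no arm comparison.* The 1.1 hypotheses compare VLNC with NNC, the 8.3 models cover between-subject treatment-related change, and 8.2 cites an N for the interaction. Only the deciding term is unnamed. The paired t-tests described as across groups may be pooled or compared by arm; the wording does not settle it. False-positive rates for Aim 1 computed on the pooled reading would not be a property of the plan.
- *That dependence has no clean baseline.* MNWS, QSU and cigarettes per day, all listed in 8.3, have one.
- *That the endpoint's own questionnaire is mistimed.* Section 1.2 names no questionnaire.
- *That the late baseline must shrink the effect.* Section 11.0 says reduced nicotine may cause withdrawal symptoms, so early scores could move either way.

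**Conclusion.** The concern holds for dependence. One of two primary endpoints has no listed between-arm analysis, so the plan as written gives no randomised result for it. That conclusion rests on the text alone.

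The timing point is narrower: it applies to the Nicotine Dependence questionnaire, where the baseline may be affected by treatment to an unknown degree and in an unknown direction.

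A properly specified comparison would have modest power. For an assumed 0.5 SD difference it runs from 52% unadjusted to 80% with ANCOVA at ρ = 0.7 (50/25), and from 43% to 71% at 40/20. At alpha 0.025 and ρ = 0.5 it is 53% and 43% respectively. The effect size, the correlations and the alpha split are all assumptions. For Aim 1, only a clarification of wording is needed.

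**What to change.** 1. Name one dependence outcome in 1.2 and compare arms on it at week 6 by ANCOVA on arm, pre-dispensing baseline and gender (the stratification factor in 7.4.3).
2. If recruitment is open, give the Nicotine Dependence questionnaire at the remote screen as well; Remote visit 3 already repeats it around week 6. Otherwise choose an outcome with a same-scale baseline before dispensing: cigarettes per day, with a stated plan for missing logs, or MNWS or QSU, stating that both values follow 14 hours of abstinence.
3. State how the two primary endpoints share alpha, are ordered, or are both required.
4. If dependence is meant only as a correlate, correct 1.2 instead of steps 1 to 3.
5. As a clarification, name the VLNC-minus-NNC difference in 6-week-minus-baseline change as the deciding Aim 1 test. If the paired t-tests are pooled pre/post tests, label them descriptive.

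Cost: SAP wording, at most two degrees of freedom (at ρ = 0.5 and 50/25, power moves from 0.643 to 0.642 when gender is added), and one existing questionnaire given earlier. No new visit is needed. Splitting alpha, if chosen, costs power as shown above.
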